Patients will be selected and included during consultations with the investigating dental surgeons. Once a diagnosis requiring first-level endodontic treatment or re-treatment is given, the investigator will offer the patient the opportunity to participate in the study and will seek to obtain their consent after introducing them to the study, in accordance with Good Clinical Practice.

Once the endodontic treatment has been completed and the permanent coronal restoration has been carried out, patients will be monitored regularly for 2 years, with 3 follow-up visits scheduled: at 6 months, 12 months and 24 months. At each visit, a clinical examination and a retro-alveolar X-ray will be carried out to assess the results of the treatment.

At the end of the 24-month follow-up period, only patients treated with the PA1704 ready-to-use filling material will be offered the option of continuing

the clinical follow-up for up to 5 years; in which, at their annual dental check-up in the 4th and 5th years following the endodontic treatment, a clinical examination and a retro-alveolar X-ray will be performed to assess the results of the treatment.

Study procedure:

V0 — Selection visit:

- diagnosis (preoperative 2D retro-alveolar X-ray) and verification of eligibility,
- oral information about the trial and delivery of patient information and consent form,

V1 — Enrolment visit

- Collection of written consent
- Recording in the eCRF of **patient characteristics at enrolment** (sex, age, oral-dental status, history and treatments) AND characteristics of the **tooth to be treated** [tooth number, number of canals to be filled, initial or repeat endodontic treatment, pulpal and periapical diagnosis, preoperative pain (if root canal preparation and filling are carried out over several sessions, preoperative pain is recorded at the start of each session)].
- Randomization (PA1704 vs BioRoot™ RCS filling material).
- Endodontic treatment in 1 or 2 sessions depending on each practitioner's usual practice and the clinical situation (initial or repeat endodontic treatment): 1) removal of the old filling material in case of retreatment, 2) root canal preparation, 3) standardized root canal obturation (obturation cements will be used with Gutta-Percha cones in accordance with the manufacturer's recommendations using the single cone technique or cold lateral condensation),
- Immediate post-operative **X-ray check** (=T0) to verify the level of the apical filling.

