3.1.2. Efficacy of endodontic treatment

It can take several years for a periapical lesion to heal completely, so that the success of the treatment can be assessed. According to Ørstavik (1996) and the recommendations of the European Society of Endodontology (2006), a minimum period of 12 months is essential to assess the efficacy of a treatment on the basis of clinical and radiological criteria. Ørstavik (1996) reported that the peak incidence of healing occurs at 1 year; he also showed that 88% of roots in which the extent of the radiolucency had decreased after 4 years had already begun to regress during the first year. Extending the follow-up to 3 or 4 years may be necessary to record a stable treatment result (Friedman 2002). However, the longer the follow-up period after endodontic treatment, the lower the percentage of patients who present for their follow-up visit (recall rate), which may invalidate the trial results (Friedman 2002). Ørstavik et al. (2004) found that patients who were absent at the follow-up visit demonstrated more clinical symptoms and felt that their treatment had failed.

Therefore, all root canal treatments should be **evaluated clinically and immediately by X-ray at 1 year and then periodically,** depending on the situation (ANDEM 1996; European society of endodontology, 2006).

To assess the success of a treatment, Wu et al. (2011) suggest measuring **effective or ineffective treatment rates**, rather than using the terminology "success and failure rates":

- An effective endodontic treatment is defined by the absence of symptoms and partial or complete healing of the apical lesion,
- An ineffective treatment is defined as the development of a lesion or the increase in size of a
 pre-existing lesion, whether or not associated with the emergence of clinical signs or symptoms
 in the patient; this unfavorable development leads to the endodontic treatment having to be
 repeated.
- If the tooth is asymptomatic and the size of the apical lesion has not changed significantly, the efficacy of the treatment is considered **uncertain** and monitoring must continue.

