 - o 5th campaign: After approximately 5 years of clinical follow-up of the patients treated with the PA1704 MD, a centre-blind review of the 5-year follow-up image.

By combining the responses relating to the radiological and clinical criteria, 3 levels of treatment efficacy are obtained: Effective treatment, Ineffective treatment, Efficacy uncertain (see table below).

Treatment efficacy will be evaluated using 2 complementary approaches:

- Main analysis on soft criteria: the rates of effective or uncertain treatment are compared with the rates of ineffective treatment,
- Secondary analysis based on strict criteria: rates of effective treatment are compared with rates of uncertain or ineffective treatment.

ТО	Check-ups at 6, 12 and 24 months							
Radiological criteria	Radiological criteria (blind reviewer)	Clinical criteria (investigator)	Conclusion Treatment efficacy rate					
No lesions	No lesions (complete healing)	asymptomatic, functional tooth	Effective treatment					
No lesions	Appearance of lesion (failure)	asymptomatic, functional tooth	Ineffective treatment					
No lesions	Appearance of lesion (failure)	symptomatic, non- functional tooth	Ineffective treatment					
Presence of lesion	No lesions (complete healing)	asymptomatic, functional tooth	Effective treatment					
Presence of lesion	Reduction in lesion size (incomplete healing)	asymptomatic, functional tooth	Effective treatment					
Presence of lesion	Reduction in lesion size (incomplete healing)	symptomatic, non- functional tooth	Efficacy uncertain					
Presence of lesion	Stabilization of lesion size	symptomatic or non- functional tooth	Ineffective treatment					
Presence of lesion	Stabilization of lesion size	asymptomatic tooth, functional tooth	efficacy uncertain					
Presence of lesion	Increase in lesion size (failure)	symptomatic or non- functional tooth	Ineffective treatment					
Presence of lesion	Increase in lesion size (failure)	asymptomatic tooth, functional tooth	Ineffective treatment					

Table 4: Evaluation of the efficacy of endodontic treatment based on clinical and radiological criteria.

✓ Equipment to be used to evaluate clinical trial variables and arrangements for monitoring maintenance and calibration.

Apart from the radiology equipment connected to a computer, no specific equipment is needed to collect the outcome measures.

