6.5.2. Visit procedure

Each patient enrolled in the study will be followed-up with for 2 years or 5 years, depending on the randomized group:

- Arm of the comparator medical device BioRoot™ RCS: Once the endodontic treatment has been completed and the permanent coronal restoration has been carried out,3 follow-up visits are scheduled: A visit at 6 months,12 months, and 24 months.
- Arm of the investigational medical device PA1704: Once the endodontic treatment has been completed and permanent coronal restoration has been carried out, there will be 5 follow-up visits: A visit at 6 months, 12 months and 24 months; at the end of the 24-month follow-up period, patients will be offered 2 further visits: One in the 4th year after the endodontic treatment (approx. 3.5 years ± 6 months) and one visit in the 5th year after the endodontic treatment (approx. 5 years ± 6 months).

For each patient and at each visit, a clinical examination and a retro-alveolar X-ray will be performed to assess the results of the treatment. The procedure for taking the images is described in Section "Equipment to be used to evaluate clinical trial variables and arrangements for monitoring maintenance and calibration." of Chapter 6.1.

The procedure for the visits is as follows (see the diagram in section Table 7):

V0 — Selection visit:

— diagnosis (including a preoperative 2D retroalveolar X-ray; the entire tooth — from the *crown to the root to the apex* — must be visible in the image; the image must be uploaded to the eCRF after the patient has been included; no blind review of this image),

- verification of eligibility,
- information about the trial and handover of consent form,

Patients will be included after diagnosis of the need for endodontic treatment.

V1 — Enrolment visit (T0)

- Collection of written consent
- Recording of patient characteristics at enrolment:
 - Sex, age, history and treatment at enrolment, smoking status,
 - Oral-dental health: DMFT index and CPITN index (record each value and then the CPITN index will be calculated automatically in the eCRF),
 - Characteristics of the tooth to be treated: tooth number, number of canals to be filled, indication for initial or repeat endodontic treatment, pulp diagnosis (irreversible pulpitis, necrotic pulp, living pulp with indication for ET) and periapical diagnosis (presence of an apical lesion, symptomatic tooth), preoperative pain (see pain record in the patient record detailed in the paragraph below).

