- **Retro-alveolar X-ray check** to evaluate the results of endodontic treatment at 24 months: 1) density of the root canal filling (radiopacity + presence of voids), 2) progress of resorption of the extruded material where appropriate, 3) apical lesion (absence/appearance/still present compared with TO) and progress of the size of an existing lesion (reduction, stabilization or increase).

Upload the 24-month follow-up retro-alveolar image to the eCRF (reminder: the entire tooth – from the *crown to the apex, including the root* – must be visible in the image; see Chapter 6.1).

— Where appropriate (in the event of the appearance of a lesion or an increase in the size of a pre-existing lesion), notification of ET failure by the investigator: schedule retreatment.

For patients in the PA1704 group whose endodontic treatment is effective at 24 months: Offer to continue clinical follow-up for up to 5 years: Inform patients about the study (dedicated information note) and provide them with a consent form.

— Complete the end-of-study form at the end of the eCRF for patients whose clinical follow-up has been completed (all patients in the BioRoot™ RCS group are followed-up with for up to 24 months, and patients in the PA1704 group who decline to continue the clinical follow-up for up to 5 years or for whom treatment failure is notified at 24 months).

PA1704 arm: V6 — Clinical follow-up visit at 3.5 years (± 6 months) — Standard practice

- **Clinical examination**: Verification of the functional status of the treated tooth and percussion test (lateral and axial),
- Recording of AEs.
- **Retro-alveolar X-ray check** to evaluate the results of endodontic treatment at 3.5 years: 1) density of the root canal filling (radiopacity + presence of voids), 2) progress of resorption of the extruded material where appropriate, 3) apical lesion (absence/appearance/still present compared with T0) and progress of the size of an existing lesion (reduction, stabilization or increase).

Upload the 3.5-year follow-up retro-alveolar image to the eCRF (Reminder: The entire tooth – from the *crown to the apex, including the root* – must be visible in the image; refer to Chapter 6.1).

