7.7. Statistical methods

The statistical methods are based on the following elements and will be detailed in the Statistical Analysis Plan.

7.7.1. Sample description:

The description of the subjects enrolled who completed the trial and those enrolled who left prematurely will be presented using a table of absolute (N) and relative (%) frequency. Reasons for premature discharge and deviations from the protocol will be listed.

7.7.2. Descriptive analyses:

Clinical data collected at enrolment and at each visit will be described. Descriptive statistics will be presented according to the nature of the criterion analyzed:

- Quantitative variable: sample size, number of missing data sets, mean, standard deviation, median, minimum and maximum;
- Qualitative variable: absolute frequencies (N) and relative frequencies (%) per class in each group, number of missing data.

Graphs will be provided for each variable.

7.7.3. Comparative analyses:

A comparison of 2 independent means will be made using the Student's t-test; if the variances are unequal (verified by the Fisher's test), use the Welch's test instead of the Student's test. If the conditions for applying the Student test are not met (n < 30), the non-parametric Wilcoxon test is used.

2 independent percentages are compared using Pearson's Chi-2 test. If the conditions for application are not met (at least one theoretical number < 5), Fisher's exact test is used.

7.7.4. Analysis of primary performance criterion:

As a reminder, the primary performance criterion is the efficacy rate at 24 months of treatment based on clinical criteria assessed by the investigator (tooth functionality and pain level) AND radiological criteria assessed blind by independent reviewers (complete healing, reduction of lesions, failure). In the event of failure at 6 or 12 months, the patient will be considered to have failed at 24 months.

The primary criterion will be analyzed using 2 approaches, in accordance with the literature:

- **Primary analysis of soft criteria**: treatment rates with complete or incomplete cure are compared against failure rates;
- **Secondary analysis of strict criteria**: treatment rates with complete healing are compared against rates of failure or incomplete healing (complete healing can take up to 4 or 5 years).

The comparison of efficacy rates between the 2 groups will be carried out using the Dunnett and Gent χ^2 test (Dunnett CW and Gent M 1977; Elie C et al 2008).

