No interim analysis of the primary criterion is planned. The main analysis will only be carried out after the 2-year follow-up of all patients enrolled.

Two interim analyses of the secondary criteria have been planned. These will be carried out after 6 and 12 months' follow-up for all included patients.

The alpha risk will not be inflated, as the main criterion will not be analyzed in the interim analyses. Therefore, no alpha risk adjustment method is required. The final analysis will focus on the primary and secondary criteria.

For patients treated with the PA1704 ready-to-use filling material and who agree to be followed-up with for up to 5 years, a non-comparative descriptive analysis of secondary performance and safety criteria at 3.5 years and 5 years will be carried out at the end of their participation.

7.7.8. Criteria for stopping the clinical trial from a statistical point of view:

None. Interim analyses are only used to collect data on secondary criteria before the end of the study. The conclusion on the non-inferiority of PA1704 compared to BioRoot™ RCS will only be made on the final analysis at 2 years.

7.7.9. Changes to the statistical analysis plan:

The statistical analysis plan will be drawn up before the first interim analysis is carried out. The initial analysis strategy may undergo minor modifications following each data review, and the new statistical analysis plan will be described in detail at that time.

7.7.10. Specification of sub-groups for further analysis:

The following sub-group analyses will be carried out, at least on the PP population, during the final analysis at 2 years. Other factors not considered in this protocol may be added in the Statistical Analysis Plan.

- For the primary criterion, the rate of effective treatment at 2 years:
 - Prognostic factors at enrolment
 - Presence or absence of a periapical lesion,
 - Indication for endodontic treatment: initial versus repeat endodontic treatment,
 - Factors related to the surgical procedure
 - Type of rinse solution used to finalize root canal disinfection,
 - Operating techniques used: technical platform used (whether or not a microscope was used), manual files versus continuous rotation versus alternative rotation.
- Post-operative pain:
 - Operating techniques used: manual files versus continuous rotation versus alternative rotation.
 - Initial pulp pathology (pre-existing inflammatory situation or necrosis or live pulp),

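### The 24-month visit text offers the 5-year extension only where PA1704 treatment is effective, so teeth rated uncertain have no instruction and the population behind the 3.5- and 5-year rates is undefined

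*Combined protocol and SAP*

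**What the plan says.** The passages that decide who enters the extension differ.

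- **Section 6.5.2, V5, offer:** "For patients in the PA1704 group whose endodontic treatment is effective at 24 months: Offer to continue clinical follow-up for up to 5 years". The information note and consent form for the extension are handed over at this visit.
- **Section 6.5.2, V5, close-out:** in the PA1704 arm the end-of-study form is completed for patients "who decline to continue the clinical follow-up for up to 5 years or for whom treatment failure is notified at 24 months".
- **Section 6.5.2, introduction, PA1704 arm:** "at the end of the 24-month follow-up period, patients will be offered 2 further visits". No efficacy condition is attached.
- **Synopsis, study procedure:** "only patients treated with the PA1704 ready-to-use filling material will be offered the option of continuing". Again there is no efficacy condition.
- **Section 7.7.7, late analysis:** "For patients treated with the PA1704 ready-to-use filling material and who agree to be followed-up with for up to 5 years", a non-comparative description is planned. Agreement is the only condition.

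Table 4 in Section 6.1 sorts each tooth as effective, ineffective or uncertain. The same section groups the first and third for the main analysis: "Main analysis on soft criteria: the rates of effective or uncertain treatment are compared with the rates of ineffective treatment".

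**The concern.** A tooth rated uncertain at 24 months fits neither V5 sentence. It is not effective in the Table 4 sense, so no offer is prescribed. It is neither a refusal nor a notified failure, so no close-out is prescribed. A site that follows the offer sentence to the letter would not hand over the extension consent form, and would collect nothing on that tooth at 3.5 or 5 years.

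Efficacy of PA1704 at those two times is a stated secondary objective (Section 5.1), and Section 3.4 says the long-term data support the marking application. If entry depends on being effective at 24 months, the late rates describe a group already selected on a good result. Some teeth would count as successes in the main 24-month analysis and then disappear. No later choice of denominator can supply an outcome that was never observed.

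**Working it through.** **1. Which Table 4 rows are at stake**

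| Lesion at follow-up (lesion present at T0) | Tooth | Table 4 class | Offered the extension on a literal V5 reading? |
|---|---|---|---|
| Healed | asymptomatic, functional | effective | yes |
| Shrinking | asymptomatic, functional | effective | yes |
| Shrinking | symptomatic, non-functional | uncertain | no instruction |
| Stable | asymptomatic, functional | uncertain | no instruction |
| Stable | symptomatic or non-functional | ineffective | no |
| Enlarging | any | ineffective | no; the visit text has failure notified |

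Only the two uncertain rows are in doubt.

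**2. Who can apply the term at V5**

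The radiological column of Table 4 is the blind reviewers' reading. Section 6.1 schedules the 24-month review after all patients have completed 24 months, so the final class does not exist when the offer is made. The V3, V4, V6 and V7 texts each include an efficacy evaluation by the investigator. The V5 text does not, although Table 7 marks one at that visit. The word effective at V5 therefore has no stated definition and no stated assessor.

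**3. The plan's own figures**

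The documents give no sample size for the extension and no expected share of uncertain teeth. The 24-month sample size reproduces from Section 7.2 (90% in both arms, margin 13 points, one-sided 5%) with the 80% power in Section 7.3:

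n = 2 × 0.90 × 0.10 × (1.645 + 0.842)² / 0.13² = 65.85, rounded up to 66 per group; 66 × 1.20 = 79.2, rounded up to 80.

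Nothing in this point changes those numbers. They supply only the 80 patients and the 90% rate used below.

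**4. Illustration for the late rate**

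Assumptions, none of them from the documents except the 80 and the 90%:

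- 80 × 0.90 = 72 PA1704 patients without failure at 24 months, ignoring losses.
- U of them are uncertain: 4 (5% of 80) or 8 (10% of 80).
- 5% of effective teeth fail by 5 years, and a fraction f of uncertain teeth fail.

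Rate with effective teeth only: 95%.
Rate with uncertain teeth included: [(72 − U) × 0.95 + U × (1 − f)] / 72.

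| U | f = 0 | f = 0.5 | f = 1 |
|---|---|---|---|
| 4 | (64.6 + 4)/72 = 95.3% | (64.6 + 2)/72 = 92.5% | 64.6/72 = 89.7% |
| 8 | (60.8 + 8)/72 = 95.6% | (60.8 + 4)/72 = 90.0% | 60.8/72 = 84.4% |

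The difference from 95% is (U/72) × (f − 0.05). It changes sign at f = 5%: below that, leaving out uncertain teeth understates the late rate. With U = 12 (15% of 80) the range is 79.2% to 95.8%. Losses spread evenly over the classes leave these percentages unchanged.

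**The case against.** The strongest reply is that nothing is actually excluded. The synopsis, the Section 6.5.2 introduction and Section 7.7.7 set no efficacy condition. Section 7.4 describes 5-year follow-up for the PA1704 arm, and the withdrawal criteria in Section 6.3 list failure needing repeat treatment, not uncertainty. In the V5 text the offer follows directly after the notification of failure, so effective may simply mean not notified as failed. That sense agrees with the close-out sentence and with the soft criterion. This much stands: a reader might infer that uncertain teeth are barred from the extension, and the documents do not settle that. What they show is a conflict and an undefined term. The reply does not remove the conflict, because Section 6.1 keeps effective and uncertain as separate labels even where it groups them.

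Three further inferences are tempting and should not be drawn.

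- **That the extension cannot show how unresolved lesions end.** A shrinking lesion on an asymptomatic, functional tooth is effective in Table 4 and is offered the late visits on any reading. The remark in Section 7.7.4 that "complete healing can take up to 4 or 5 years" is attached to incomplete healing, which is largely this retained group.
- **That the protocol orders continued monitoring of every uncertain tooth.** Section 3.1.2 does say that "the efficacy of the treatment is considered uncertain and monitoring must continue", but this is background reporting a cited classification. It covers the asymptomatic tooth with an unchanged lesion, not the other uncertain row, and it is not a visit rule.
- **That the late rate is overstated by a known amount.** The 2.5 and 5 point gaps in the illustration are the f = 0.5 column only. With f = 0 the sign reverses.

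It is also true that the late results are for one arm and descriptive only.

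**Conclusion.** The inconsistency is real and should be corrected. The V5 offer sentence, its own close-out sentence, the synopsis, the Section 6.5.2 introduction and Section 7.7.7 do not define one population for the extension. The literal V5 reading would select the 3.5- and 5-year cohort on 24-month success.

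The effect on the late rate cannot be determined from the documents. Under the assumptions shown (72 non-failures, 4 to 8 uncertain, 5% late failure among effective teeth), including the uncertain teeth gives about 84% to 96%, against 95% without them. The gap could be negligible, more than 10 points, or slightly in the other direction, and without the late visits the trial could not tell which. The 24-month non-inferiority comparison and its sample size are untouched.

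**What to change.** 1. Reconcile the synopsis, the Section 6.5.2 introduction, the V5 offer and close-out sentences, and Section 7.7.7, so that all use one population and every PA1704 patient at V5 falls under exactly one instruction.
2. State whether effective in the V5 offer means the Table 4 class or the soft criterion (effective or uncertain). State also that the investigator's V5 assessment applies, since the blind reading is not yet available.
3. Report the 3.5- and 5-year class by 24-month class, with the denominator given. If the sponsor keeps the narrower population, label the late rates as conditional on effective treatment at 24 months.

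The cost is a wording amendment handled under Section 9 and one descriptive table. If the uncertain class is included, there are also a few more V6 and V7 study visits with X-rays for patients who consent. The wording needs to be settled before the V5 visits, because late data on patients who were never offered the extension cannot be collected afterwards. No treatment or retreatment rule is proposed.
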